### 9.1.3. Procedure for Handling Drug Spills

Precautions for drug handling of cytotoxic agents should be followed for NMS-03592088. In case of opening of the capsules, avoid contact or inhalation. In case of skin contact, the affected area should be washed with plenty of water or soap and water. Any contaminated clothing should be removed. In case of eye-contact, rinse thoroughly with plenty of water. Seek medical advice as soon as possible.

### 9.1.4. Storage and Stability

CCI

### 9.1.5. Source of Drug

CCI

### 9.1.6. Drug Accountability

NMS-03592088 must not be used outside the context of this protocol. Under no circumstances should the Investigator or site personnel supply study product to other Investigators or clinics, or allow the supplies to be used other than as directed by this protocol.

In this protocol the study drug may be administered to patient, according to the selected schedule, until the criteria for withdrawal as detailed in Section 10 are met. Drug accountability should continue to be performed until the patient's last dose of NMS-03592088.

Adequate records on receipt, use, return, loss, or other disposition of medication must be maintained and electronically captured in the dedicated eCRF page. If needed, specific drug accountability forms supplied by the Sponsor or designee or computer records used by the pharmacy at the investigational site, and agreed with the Sponsor or designee, can be also used to provide drug accountability information. In either case, information describing study drug supplies and their disposition, patient by patient, must be provided, signed by the Investigator (or the pharmacist or other person who dispensed the drug) and collected by the study monitor. Requisite data includes relevant dates, quantities, batches or code numbers, and patient identification for patients who received study drug. At the end of the study, after verification by the study monitor and upon authorization of the Sponsor, the unused study drug may be destroyed at the site as dictated by the appropriate standard procedures of the participating institution. Destruction must be documented. Alternatively, all unused product will be returned to the Sponsor or Manufacturer on behalf of the Sponsor. If disposed locally, all used bottles and containers of study product should be discarded according to the standard institutional policy.

## 9.2. Treatment Administration

### 9.2.1. Treatment Dose and Schedule

CCI

CCI [REDACTED]  
[REDACTED]

[REDACTED]  
[REDACTED]  
[REDACTED]  
[REDACTED]

[REDACTED]  
[REDACTED]  
[REDACTED]  
[REDACTED]  
[REDACTED]  
[REDACTED]

[REDACTED]  
[REDACTED]  
[REDACTED]  
[REDACTED]  
[REDACTED]

[REDACTED]  
[REDACTED]

[REDACTED]  
[REDACTED]

[REDACTED]  
[REDACTED]  
[REDACTED]

### 9.2.2. Duration of Treatment

Patients may continue on study treatment until disease progression, unacceptable toxicity, investigator decision, withdrawal of consent by the patient or other discontinuation criteria detailed in Section 10 are met. Note: If patient is clinically stable and has observation of blasts reduction or suspected disease stabilization in the judgment of the investigator the investigator may continue dosing after an adverse event taking into account dose modification in section 9.2.3.

A participant patient is considered to have completed the study if he/she has completed all phases of the study including the last scheduled procedure as shown in the Schedule of Events in Section 1.

### 9.2.3. Dose Modifications

Adverse events that are intolerable or severe will be managed by treatment interruption and/or dose reduction depending on the circumstance. Dose reductions and delay will be based on adverse events at least possibly related to the study drug.

Dose modifications may occur during a cycle or at the start of a new cycle. All dose modifications for the start of a new cycle should be based on the most severe toxicity observed in the previous cycle. In the event of multiple toxicities, the dose modification should be based on the worst toxicity observed (according to the NCI CTCAE v 5.0).

Any modifications to the NMS-03592088 dose should be documented in the eCRF.

#### 9.2.3.1. Re-treatment Criteria and Cycle Delay

For a patient with non- hematological toxicities, a new cycle of treatment may begin when toxicities (except for alopecia) are  $\leq$  Grade 1 or have recovered to pre-treatment status. If these conditions are not met, treatment should be delayed for 1 week and up to a maximum of 2 weeks, to allow for recovery. If, after this period, toxicities do not recover to the pre-defined level, patient will be withdrawn from the study unless the patient is demonstrating clinical benefit as agreed by the Investigator and Sponsor.

#### 9.2.3.2. Dose Reductions and Interruptions

If a patient experiences a DLT during Cycle 1, the patient should be discontinued from the study, unless the patient is demonstrating clinical benefit and can continue the treatment at a reduced dose, as agreed by the Investigator and Sponsor. If a patient experiences a non-hematological adverse event meeting DLT criteria after Cycle 1, administration of NMS-03592088 should be held until the drug related toxicity has resolved to Grade  $\leq 1$  or baseline grade. Upon resolution of the toxicity, the patient should restart study drug at the next lower dose level depending on the severity and type of toxicity observed and after discussion with Sponsor or designee. If the patient experiences persistent Grade 4 myelosuppression in the absence of disease progression, dose reduction can be considered starting from Cycle 3.

CCI

France specific: In case of G4 non hematological toxicity reoccurrence, NMS-03592088 must be permanently discontinued.

[figure not shown]
Suggested dose reduction and interruption or discontinuation criteria are described in [Table 1](#) and are provided as guidance to the Investigators.

NMS-03592088  
Protocol for Study MKIA-088-001

MKIA-088-001\_P9  
Version 9\_28 February 2024

**Table 1. Recommended Dose Modification Criteria\* for Treatment-Related Toxicity  
Observed During or Prior a Treatment Cycle**

CCI

CCI

CCI

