## 10. PATIENT WITHDRAWAL FROM STUDY PARTICIPATION

Patients may withdraw from the study at any time at their own request, or they may be withdrawn at any time at the discretion of the Investigator or Sponsor for safety, behavioral, or administrative reasons.

If a patient does not return for a scheduled visit, every effort should be made to contact him/her. In any circumstance, every effort should be made to document patient outcome, if possible. The Investigator should inquire about the reason for withdrawal, requests the patient to return for a final visit, if applicable, and follow-up with the patient regarding any unresolved adverse events.

If the patient withdraws from the study and also withdraws consent for disclosure of future information, no further evaluations should be performed and no additional data should be collected. The Sponsor may retain and continue to use any data collected before such withdrawal of consent.

Patients may continue with therapy with the study medication unless any of the following occurs:

- Disease progression or relapse at any time;  
Note: If patient is clinically stable and has observation of blasts reduction or suspected disease stabilization in the judgment of the investigator the patient may continue with dosing after an adverse event taking into account dose modification in section 9.2.3;  
Note: Patient must *discontinue treatment for failure to achieve at least partial response after 9 cycles*
- Global deterioration of health status requiring discontinuation;
- First-cycle DLT, unless the patient is demonstrating clinical benefit and can continue the treatment at a reduced dose, as agreed by the Investigator and Sponsor;
- CCI with systemic and/or bulbar impairment
- Unacceptable study drug-related toxicities incompatible with continuation of treatment with NMS-03592088 according to the judgment of the Investigator, even at a reduced dose;
- Change in the patient's medical status (including pregnancy) such that the Investigator believes that patient safety may be compromised or that it would be in the best patient's interest to stop treatment;
- Treatment delay for >14 days due to treatment related non-hematologic toxicity unless the patient is demonstrating clinical benefit as agreed by the Investigator and Sponsor;
- The patient becomes eligible for hemopoietic stem cell transplantation (HSCT)

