- Substantial deviation from specified inclusion or exclusion criteria or non-compliance by the patient with protocol requirements;

- Investigator's decision;
- Patient's refusal to continue study treatment;
- Patient lost to follow up;
- Death;
- Study terminated by Sponsor.

Patient will be withdrawn from the study in case of:

- Withdrawal of consent;
- Patient lost to follow up;
- Death;
- Study terminated by Sponsor.

Data to be collected for the end of study treatment/withdrawal are described in the Schedule of Events, reported in Section 1.

Patients will be followed for at least 28 days after the last dose of study drug for adverse events and for 18 months from patient's first study drug dose for survival status.

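### Sections 9.2.3.1 and 9.2.3.2 take patients with a Cycle 1 DLT or unresolved toxicity off the study; Section 10 takes them off the drug and goes on to require 18-month survival status

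*Protocol*

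**What the plan says.** Two sentences under treatment administration direct that patients leave the study.

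- Protocol 9.2.3.1 covers non-hematological toxicity that has not recovered after a delay of one week, extendable to two: "patient will be withdrawn from the study unless the patient is demonstrating clinical benefit", where the benefit is agreed by the Investigator and Sponsor.
- Protocol 9.2.3.2 covers a DLT in the first cycle: "If a patient experiences a DLT during Cycle 1, the patient should be discontinued from the study, unless the patient is demonstrating clinical benefit". The exception also requires that dosing can go on at a lower level.

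Protocol Section 10 deals with the same events in a list introduced by "Patients may continue with therapy with the study medication unless any of the following occurs". The list includes "First-cycle DLT, unless the patient is demonstrating clinical benefit and can continue the treatment at a reduced dose" and "Treatment delay for >14 days due to treatment related non-hematologic toxicity", the latter again with the clinical-benefit exception.

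A second, separate list in Section 10 opens with "Patient will be withdrawn from the study in case of". It has four entries: consent withdrawn, loss to follow-up, death, and termination of the study by the Sponsor. Neither DLT nor toxicity appears there. Section 10 ends by requiring adverse-event follow-up for at least 28 days from the last dose and survival status to 18 months from the first dose.

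**The concern.** Section 10 draws a clear line between stopping the drug and leaving the study. The two sentences in 9.2.3 put the same patients on the other side of that line. The sentence in 9.2.3.1 is mandatory in tone, and neither sentence points to Section 10. They are also the text a site consults when toxicity occurs.

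Three things depend on which text a site follows.

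- **Overall survival.** OS is a secondary endpoint in both phases. If follow-up ends because of toxicity, censoring may be related to prognosis.
- **Disposition.** SAP 9.1 reports reasons for treatment discontinuation and reasons for study withdrawal separately. Two sites could record the same event differently.
- **Scope.** The DLT trigger matters mainly in Phase I. The toxicity-delay trigger applies in both phases.

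The first-cycle DLT endpoint, the CRc rate and the futility rule do not depend on this wording. Unresolved serious events and unresolved drug-related events are already followed beyond the reporting period under Section 11.5.1.5. An effect on event-free survival cannot be shown, because those rules are redacted.

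**Working it through.** **Step 1: set the texts side by side.**

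| Event | Section 9.2.3 | Section 10, medication-stop list | Section 10, study-withdrawal list |
|---|---|---|---|
| Cycle 1 DLT, no agreed clinical benefit | Discontinued from the study (9.2.3.2) | Listed | Not listed |
| Non-hematological toxicity not recovered after a 14-day delay, no agreed clinical benefit | Withdrawn from the study (9.2.3.1) | Listed (delay over 14 days) | Not listed |

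The events and exceptions match, but the consequence differs. Section 10 does not name these patients in its follow-up sentence. That they stay in survival follow-up is inferred from its general wording and from their absence from the four-item list.

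**Step 2: follow-up at stake per patient.** The plan gives no figure to reproduce here. The inputs are:

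- Earliest exit under 9.2.3.1: 28-day cycle + 14-day delay = day 42, or 42/30.44 = 1.38 months.
- Horizon: 18 months from first dose (Section 10).
- Median survival: 5.6 and 9.3 months, the two arms of the gilteritinib trial described in Section 3.2, which is a different population; 3 months is an assumed low value.
- Exponential survival (assumed), with hazard h = ln 2 / median.

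Expected survival time between exit on day x and month 18, given alive at exit, is (1 − exp(−h × (18 − x/30.44))) / h.

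For x = 42 and median 5.6: h = 0.1238, remaining horizon 16.62 months, result 7.05 months, or about 214 days.

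| Median (months) | Exit day 42 | Exit day 28 (DLT at end of Cycle 1) |
|---|---|---|
| 3 | 129 days | 129 days |
| 5.6 | 214 days | 216 days |
| 9.3 | 290 days | 294 days |

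Exits after day 42 expose less.

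**Step 3: what this could do to the median (illustration only).** Assume that a fraction f of patients alive at day 42 is removed then, and that their later hazard is m times h, with h = ln 2 / 5.6. True survival after month 1.38 is

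S(t) = (1 − f) exp(−ht) + f exp(−1.38h − m h (t − 1.38)).

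Kaplan-Meier with the removed group censored at exit estimates 5.60 months in every case. The true medians are:

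| f | m = 0.5 | m = 1 | m = 2 |
|---|---|---|---|
| 10% | 5.85 | 5.60 | 5.28 |
| 20% | 6.13 | 5.60 | 4.99 |

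The largest difference is 5.60 − 4.99 = 0.61 months.

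**Step 4: compare with sampling error in one Phase II cohort (n = 40).** Expected deaths by month 18 are 40 × (1 − exp(−18h)) = 35.7. The approximate 95% interval for the median is 5.6 × exp(±1.96/√35.7), which gives 4.03 to 7.77 months. All of the illustrated medians lie inside it.

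**The case against.** The best case against is that no careful site would be misled.

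- The exception in 9.2.3.2 is about continuing treatment at a lower dose, so the natural alternative is stopping treatment. Sections 9.1.6 and 9.2.2 both defer to Section 10. This stands as evidence of intent, and it is why Section 10 is taken as the meaning.
- Section 10 says "In any circumstance, every effort should be made to document patient outcome, if possible". It also ends data collection only when a patient who withdraws from the study additionally withdraws consent to disclosure of future information. Both sentences lower the risk. The first is qualified and sits in the paragraph on missed visits and withdrawal; the second concerns withdrawal by the patient. Neither corrects the instruction in 9.2.3.
- Section 10 does not present its four-item list as exclusive, and it says of patients that "they may be withdrawn at any time at the discretion of the Investigator or Sponsor for safety, behavioral, or administrative reasons". So the conflict is not absolute. A discretionary route still does not explain a stated rule of withdrawal for events that Section 10 treats as reasons to stop medication.
- The Schedule of Events, Table 1 and the efficacy analysis text are redacted and may hold a clearer follow-up instruction or the OS censoring rule. This is a fair limit on any claim about bias. It does not remove the conflict in the visible text.
- The illustration uses assumed removal rates and hazards and concerns 9.2.3.1 exits in a Phase II cohort, whereas the DLT rule bears mainly on Phase I. That is correct. It shows scale and is not an estimate for this trial.

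**Conclusion.** The inconsistency holds as a minor error of wording in current, unredacted text. Confidence is high on the mismatch itself. The consequence is conditional: it arises only if a site follows 9.2.3 literally despite the safeguards in Section 10.

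The documents give no rate of such exits, and the OS censoring rules are redacted, so neither the size nor the direction of an OS bias can be stated. Under the assumptions shown, an exit at day 42 puts about 129 to 290 days of expected survival time per patient outside follow-up, and the illustrated effect on the median is small against the precision of one cohort. That supports the minor rating. It is still worth correcting, because the loss would be selective for toxicity and the protocol already plans the follow-up.

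**What to change.** In the two sentences of 9.2.3.1 and 9.2.3.2, replace the words *the study* with *study treatment*. Add a cross-reference to the adverse-event and survival follow-up in Section 10, and to Section 11.5.1.5 for unresolved events. The discretionary withdrawal route in Section 10 stays as it is.

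The cost is a two-word replacement in each sentence plus the cross-reference. No visits, data or analyses are added.

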#### 9.2.4. Extension Treatment

Not applicable.

#### 9.2.5. Overdose and Medication Error Instructions

There are no known antidotes for NMS-03592088 overdose. In the case of an overdose clinical care must monitor for both acute and long-term effects. The Sponsor Pharmacovigilance should be notified immediately (i.e. within 24 hours) according to procedures described in part 11.5.1.7. Study monitor should be also contacted to discuss the details of any overdose.

Medication errors are reportable irrespective of the presence of an associated AE/SAE, including:

- Medication errors involving patient exposure to the product,
- Potential medication errors or uses outside of what is foreseen in the protocol that do or do not involve the participating patient.

Whether or not the medication error is accompanied by an AE, as determined by the Investigator, the medication error and, if applicable, any associated adverse event(s) must be captured on an adverse event (AE) eCRF page (refer to Safety Assessments, Section 11.5, for further details).

### 9.2.7.2. Patient management

CCI [REDACTED]  
[REDACTED]  
[REDACTED]

[REDACTED]  
[REDACTED]  
[REDACTED]  
[REDACTED]  
[REDACTED]  
[REDACTED]

CCI [REDACTED]  
[REDACTED]

[REDACTED]  
[REDACTED]  
[REDACTED]  
[REDACTED]  
[REDACTED]

[REDACTED]  
[REDACTED]  
[REDACTED]

[REDACTED]  
[REDACTED]  
[REDACTED]  
[REDACTED]  
[REDACTED]  
[REDACTED]  
[REDACTED]  
[REDACTED]  
[REDACTED]

[REDACTED]  
[REDACTED]

[REDACTED]  
[REDACTED]  
[REDACTED]

[REDACTED]

[REDACTED]

**C** [REDACTED]

### 9.2.9. Differentiation Syndrome

Differentiation syndrome (DS) is a potentially fatal complication of effective leukemia treatments, initially reported in patients with acute promyelocytic leukemia undergoing induction therapy with all-trans retinoic acid (ATRA) or arsenic trioxide [64].

DS has been described in patients with AML receiving novel targeted therapeutics including IDH inhibitors and FLT3 tyrosine kinase inhibitors. While frequency of the event has been reported to be 14%-19% for IDH inhibitors [65;66], the event is much less frequent with FLT3 inhibitors (1% for gilterinib (Xopata®) [67]. Terminal myeloid differentiation of bone marrow blasts in association with a clinical DS has also been reported in patients treated with quizartinib [68]. CCI [REDACTED]

[REDACTED]

[REDACTED]

[REDACTED]

Symptoms of DS are non-specific and may include fever, weight gain, edema, hypotension, rash, renal dysfunction, malaise, dyspnea and pleural and/or pericardial effusions, in addition to marked neutrophil-predominant leukocytosis. DS was reported to occur as early as 1 day and up to 5 months after initiation of treatment with IDH inhibitors. Prompt identification of early signs and symptoms and intervention are essential to avoid serious complications. Therapeutic intervention may include oral hydroxyurea to mitigate leukocytosis and steroid therapy, as appropriate.

### 9.2.10. Concomitant Medications and Other Therapy

All concomitant medications and other therapies must be recorded in the eCRF. Directives for supportive care are outlined below.

#### 9.2.10.1. Antiemetics Support

In Phase I (dose escalation), emesis prophylaxis is not allowed in Cycle 1, until nausea and/or vomiting have been clearly identified as study-medication expected adverse events. In the subsequent cycles, if needed, prophylactic therapy is allowed using institutional guidelines for treatment and/or published guidelines [69,70].

#### 9.2.10.2. Antidiarrheal Support

Treatment with antidiarrheal drugs is recommended once the onset of the earliest signs of diarrhea is present. Loperamide or other antidiarrheal agents used by the Institution might be started at the occurrence of Grade 1 diarrhea (increase of < 4 stools per day over baseline; mild increase in ostomy output compared to baseline). Recommendation for Loperamide use should be taken in the following manner: 4 mg at the first onset of diarrhea, then 2 mg every 2 hours. This therapy should continue for 12 hours after the last liquid stool. Patients may take loperamide 4 mg every 4 hours during the night. In no instance should loperamide be

administered for more than 48 consecutive hours because of the risk of paralytic ileus. Patients should be instructed to refer to the center in case of diarrhea lasting > 24 hours despite optimal supportive care or diarrhea with fever.

The patients should contact the Investigator or the study nurse if they experience diarrhea for the first time during the treatment; black or bloody stools; symptoms of dehydration such as lightheadedness, dizziness, or faintness; an inability to take liquids by mouth due to nausea and vomiting; or an inability to get diarrhea under control with loperamide within 24 h. In addition to loperamide, the patients should be provided with an antibiotic therapy as per institutional guidelines. Patients should be instructed to refer immediately to the center in case of occurrence of these symptoms. Patients with colitis/ileus, neutropenic fever or infection should also be hospitalized promptly for IV antibiotic therapy.

### 9.2.10.3. Hematopoietic Support

In Phase I prophylactic use of G-CSF or initiation of erythropoietin in Cycle 1 is not recommended, but may be instituted in Cycle  $\geq 2$  in patients who are having difficulty with severe neutropenia or anemia.

Patients who have been treated for  $\geq 4$  weeks with erythropoietin prior to the first cycle may continue on the existing treatment.

Patients with neutropenic fever or infection should be hospitalized promptly for IV antibiotic therapy and may receive therapeutic CSFs as appropriate.

Red blood cell and platelet transfusions should be administered as warranted.

### 9.2.10.4. Antiacids

Patients using H2-receptor antagonists must take them between at least 12 hours before and 2 hours after a dose of NMS-03592088, antacids between at least 4 hours before and 2 hours after a dose, to avoid any potential effect on NMS-03592088 absorption.

Proton pump inhibitors (PPI) are allowed if administered between at least 10 hours before and 1 hour after the dose. Sponsor might opt to restrict further PPI use.

### 9.2.10.5. Other Permitted Concomitant Medications

CCI

MKIA-088-001\_P9  
Version 9\_28 February 2024

CCI

CCI

[REDACTED]

[REDACTED]

[REDACTED]

[REDACTED]

[REDACTED]

[REDACTED]

[REDACTED]

[REDACTED]

[REDACTED]

[REDACTED]

[REDACTED]

[REDACTED]

[REDACTED]

[REDACTED]

[REDACTED]

NMS-03592088  
Protocol for Study MKIA-088-001

MKIA-088-001\_P9  
Version 9\_28 February 2024

CCI [REDACTED]  
[REDACTED]

[REDACTED]  
[REDACTED]  
[REDACTED]  
[REDACTED]  
[REDACTED]

[REDACTED]  
[REDACTED]  
[REDACTED]

[REDACTED]  
[REDACTED]  
[REDACTED]  
[REDACTED]  
[REDACTED]

